25 PREMATURE DISCONTINUATION OF THE STUDY OR PREMATURE CLOSE-OUT OF A SITE

25.1 Decided by the Sponsor in the Following Cases:

1. In the event the results of the Clinical Trial do not appear to be scientifically convincing to the Sponsor;
2. If the aim of the Clinical Trial has become outdated or is no longer of interest;
3. If the information on the product leads to doubt as to the benefit/risk ratio;
4. If the Investigator has received from the Sponsor all Investigational Product, means and information necessary to perform the Clinical Trial and has not included any patient after a reasonable period of time mutually agreed upon;
5. In the event of breach by the Investigator of a fundamental obligation under this agreement, including but not limited to breach of the Clinical Trial Protocol, breach of the applicable laws and regulations or breach of the ICH guidelines for GCP;
6. If the total number of patients are included earlier than expected; In any case the Sponsor will notify the Investigator of its decision by written notice.

25.2 Decided by the Investigator

The Investigator must notify (30 days' prior notice) the Sponsor of his/her decision and give the reason in writing. In all cases (decided by the sponsor or by the Investigator), the appropriate Ethics Committee(s) (IRB/EC) and Health Authorities should be informed.

26 CLINICAL TRIAL PROTOCOL AMENDMENTS

Any protocol amendments will be added as stand-alone documents. In addition, any and all revisions dictated by the amendments will be made in the protocol. Each time a protocol is amended, a new amended version date will be added to the cover page.

All appendices attached hereto and referred to herein are made part of this Clinical Trial Protocol. The Investigator should not implement any deviation from, or changes of the Clinical Trial Protocol without agreement by the sponsor and prior review and documented approval/favorable opinion from the IRB/EC of an amendment, except where necessary to eliminate an immediate hazard(s) to clinical trial patients, or when the change(s) involves only logistical or administrative aspects of the trial. Any change agreed upon will be recorded in writing, the written amendment will be signed by the Investigator and by the Sponsor and the signed amendment will be filed with this Clinical Trial Protocol. Any amendment to the Clinical Trial Protocol requires written approval/favorable opinion by the IRB/EC prior to its implementation, unless there are overriding safety reasons. In some instances, an amendment may require a change to the Informed Consent Form. The Investigator must receive an IRB/EC approval/favorable opinion concerning the revised Informed Consent Form prior to implementation of the change.

27 APPENDIX A-Schedule of Events

Visit name (Day)	Part 1					Part 2				
	Visit 1	Visit 2	Visit 3	Visit 4	Visit 5	Visit 1	Visit 2	Visit 3 ¹³	Visit 4 ¹⁴	
	Screening (Day -1)	Baseline (Day 0)	Week 2 (Day 14)	Follow-up #1 (Day 21)	Follow-up #2 (Day 42)	Screening (Day -1)	NAC titration (Day 0)	NAC #1 (Day 14)	NAC #2 (Day 28)	
Visit Window, in Days	-21 to 0	-3 to 1	+/-3	+/-3	+/-3	-21 to 0	+/-3	+/-3	+/-3	
Informed Consent ¹	X					X				
Inclusion/Exclusion Criteria ²						X				
Demographics						X				
Medical History						X				
Concomitant Medications				X	X	X		X	X	
HR, BP, and respiratory rate	X	¹⁵		X	X	X		X	X	
Brief Physical Exam	X	X	X	X	X	X	X	X	X	
Body Weight	X		X	X	X	X		X	X	
Height	X					X				
Allergen Skin Test (Skin Prick Test)						X ²¹				
Blood Collection for IgE						X ²¹				
ABPM ³		X	X							
Randomization ⁴								X		
Nasal inspection ⁵	X	X ¹⁵	X	X	X	X	X	X	X	X
NAC							X	X	X	
12-lead ECG	X		X		X					

Delivery of Investigational Product		X						X		
Investigational Product application								X	X	
Investigational Product compliance		X						X	X	X
Counseling ⁶								X		X
Laboratory Testing ⁷	X		X		X	X			X	X
Urinary pregnancy test ⁸	X					X				
Safety AEs	X	X	X	X	X	X	X	X	X	
Nasal fluid ⁹			X		X			X ¹⁶	X ¹⁶	X
Blood collection ¹⁰		X	X		X			X ¹⁷	X ¹⁷	X
Peak nasal inspiratory flow		X	X	X	X		X ²²	X ¹⁸	X ¹⁸	X
Intranasal nitric oxide		X	X	X	X		X	X ¹⁹	X ¹⁹	X
Nasal inflammation score ¹¹		X	X	X	X		X	X ¹⁹	X ¹⁹	X
Study diary ¹²	X	X	X	X	X	X	X ²²	X ²⁰	X ²⁰	X
Subject satisfaction survey					X				X	

1. Informed consent can be obtained up to 21 days prior to the baseline visit.
2. Inclusion and exclusion criteria will be reviewed at Screening and at Baseline visit to make sure nothing changed.
3. Ambulatory Blood Pressure Monitoring for 24 hours to be performed for 24 hours prior to baseline and Week 2 visits. Subjects to visit site 24 hours prior to baseline and Week 2 visits to initiate ABPM. ABPM removal (after 24 hour measurement) at Visits 2 and 3 followed by evaluation of technical success/failure criteria.
4. Subject's demographic data and medical history are blinded to the statistician.
5. Nasal inspection will be performed by clinical examination of the nasal mucosa, sinuses, and upper airway.
6. Subjects will be counseled on the application of the nasal spray for the duration of the study.

7. Fasting blood sample for a comprehensive metabolic panel, complete blood count, chemistry, lipid panel, and liver function test-15 ml; include urinalysis. Patients should fast for at least 8 hours before the test. Blood will be shipped to the central lab for processing.
8. Urine pregnancy test to be done on WOCBP.
9. Nasal fluid will be collected at baseline, treatment, and follow-up visits for inflammatory cytokines during Part 1. Additionally, they will be collected during challenge visits per schedule of events. Optionally, samples may be evaluated for nasal microbiome (e.g., PCR) to confirm presence of B244.
10. Blood samples for biomarkers will be collected and processed on site. Serum and plasma samples will be frozen onsite and shipped to the Central lab for storage.
11. Nasal inflammation score assessment based on otoscope measurement.
12. Subjects will be asked to fill out a daily treatment diary during screening, baseline, treatment, follow-up, and challenge period for dosing, nasal symptom scores (TNSS) and AEs.
13. Subjects will have their basic health checks and baseline assessments (intranasal fluid, PNIF, intranasal nitric oxide, and nasal inflammation score), challenged with NAC #1, challenge baseline assessments made (e.g., TNSS, PNIF, nNO, intranasal fluid, nasal inflammation score), and randomized .
14. Subjects will be challenged with NAC #2 followed by assessments.
15. Pre and post first dosing.
16. To be completed pre (0 min) and post NAC (20 and 60 min).
17. To be completed post NAC (120 min).
18. To be completed pre (-30 and 0 min) and post NAC (15, 30, 60, and 120 min).
19. To be completed pre (0 min) and post NAC (120 min).
20. TNSS to be completed pre (-30 and 0 min) and post NAC (15, 30, 45, 60, 90, and 120 min).
21. Perform either skin prick test or IgE test at screening unless documentation of a positive test in the past 12 months can be provided for either method.

22. To be completed pre (-30 and 0 min) and post NAC (15, 30, 45, 60, 90, and 120 min for TNSS and 15, 30, 60, and 120 min for PNIF).

## Document History

Version Number	Author	Date	Change
1.0	[name]	03JAN2018	Initial Version

## Glossary of Abbreviations

ABPM	Ambulatory Blood Pressure Monitoring
AE	Adverse Event
ANCOVA	Analysis of Covariance
BMI	Body Mass Index
CTR	Clinical Trial Report
eCRF	Electronic Case Report Form
MedDRA	Medical Dictionary of Regulatory Activities
NAC	Nasal Allergen Challenge
nNO	Intranasal Nitric Oxide
PNIF	Peak Nasal Inspiratory Flow
PT	Preferred Term
SAE	Serious Adverse Event
SAP	Statistical Analysis Plan
SAR	Seasonal Allergic Rhinitis
SAS®	Statistical Analysis Software
SOC	System Organ Class
TEAE	Treatment Emergent Adverse Event
TNSS	Total Nasal Symptom Score
WHO	World Health Organization

## 1. Introduction

### 1.1. Scope

This document contains detailed information to aid the production of the Clinical Trial Report (CTR) including summary tables and listings for trial ARB244-001. The contents of this document were reviewed by the sponsor AOBiome, LLC., and the trial biostatistician at Integrium.

### 1.2. Study Background/Plan

This is a prospective, controlled, double blind, single center, randomized, 3 arm, parallel assignment, phase 1b/2a study to assess the safety, tolerability, and preliminary efficacy of B244 delivered as an intranasal spray in healthy volunteers and subjects with seasonal allergic rhinitis. This will be a 2-part study. In Part 1, safety and tolerability will be evaluated during 14 days of study treatment twice-a-day followed by 4 weeks of follow-up in healthy volunteers. In Part 2, preliminary efficacy will be evaluated in subjects with a history of seasonal allergic rhinitis outside of the local pollen season.

Part 1 (safety and tolerability evaluation in healthy volunteers) will enroll 24 subjects. Up to 12 subjects per dose cohort (n=8 active n=4 vehicle) will be enrolled, with a target of 20 subjects completed (10 subjects per dose cohort) assuming a 16.7% drop out rate.

Subjects will be dispensed study medication for 14 days of at home dosing. While at home, subjects will dose twice daily (am and pm), and record their dosing, any occurrence of an AE, and Total Nasal Symptom Score (TNSS) using a study diary. In addition to the screening, pre-dose and initial dose visits, subjects will be asked to visit the site at Day 14 (Week 2) and at follow-up visits at Day 21 (Week 3) and Day 42 (Week 6) for safety assessments and will additionally obtain Peak Nasal Inspiratory Flow (PNIF), intranasal fluid (collected on days 14 and 42), intranasal nitric oxide (nNO) and nasal inflammation score.

During the 2 week safety phase (Part 1), a continuous Ambulatory Blood Pressure Monitoring (ABPM) device will monitor blood pressure of each subject for 24 hours at baseline and Day 14. ABPM would be worn for 24 hours prior to the baseline visit and again for 24 hours prior to the Day 14 visit.

Part 2 (preliminary efficacy evaluation in subjects with a history of SAR to ragweed pollen) will enroll 42 subjects. Up to 14 subjects per arm ( $1 \times 10^9$  cells/ml;  $4 \times 10^9$  cells/ml or vehicle) will be enrolled, with a target of 12 subjects per arm for a total of 36 subjects completed, assuming a 10-15% dropout rate.

Safety and tolerability will be assessed in subjects with allergic rhinitis by reporting of AEs, physical examination and vital signs (blood pressure, heart rate, respiratory rate) during 14 days of treatment.

A preliminary efficacy assessment will be performed in response to nasal allergen challenge (NAC) in a prophylaxis treatment setting.

Subjects will be asked to report for a screening visit (Visit 1) and if all inclusion/exclusion criteria are met, subjects will be asked to report for a NAC titration (ragweed pollen nasal

allergen titration) visit to administer a single provocative challenge dose for each subject (Visit 2). Subjects will then return 14 days after the washout period for basic health checks and baseline assessments (intranasal fluid, TNSS, PNIF, intranasal nitric oxide, and have a nasal inflammation score) followed by confirmatory NAC (NAC #1) (Visit 3). During this time subjects will use a study diary to complete TNSS at -30 (30 minutes prior to NAC), 0 (baseline prior to NAC), 15, 30, 45, 60, 90 and 120 minutes. PNIF at -30, 0, 15, 30, 60 and 120 minutes will also be obtained. TNSS is the sum of four individual symptom scores (running nose, congestion, itchy nose and sneezing) rated on a four point scale (0-3). Subjects will also provide samples for intranasal fluid at 0, 20 and 120 minutes, measure intranasal nitric oxide (nNO) and have a nasal inflammation score assessed by the investigator using a nasal otoscope at 0 and 120 minutes, in addition to blood collection at 120 min for biomarkers. Randomized subjects will be dispensed study medication for 14 days of at home dosing. While at home, subjects will dose twice daily (am and pm), and record their dosing, and any occurrence of an AE and TNSS using a study diary.

Subjects will return to the clinic for the last dose following the 14 days of at home dosing for their final visit (Visit 4). During this time subjects will again have their baseline assessments and be exposed to ragweed pollen challenge (NAC #2), and will use a study diary to complete TNSS at -30, 0, 15, 30 45, 60, 90 and 120 minutes and PNIF at -30, 0, 15, 30, 60 and 120 minutes. Prior to and 20 and 120 minutes after NAC #2, subjects will additionally provide samples for intranasal fluid, and have nNO measured and nasal inflammation score assessed by the investigator using a nasal otoscope at 0 and 120 min, in addition to blood collection at 120 min for biomarkers.

### **1.3. Trial Objectives and Purpose**

The primary objective of the study is to assess the safety and tolerability of B244 relative to vehicle in healthy volunteers during 14 days of treatment and up to 28 days of follow-up.

The secondary objectives of the study are:

- To evaluate the efficacy of B244 relative to vehicle in treating Total Nasal Symptom Score (TNSS) in subjects with seasonal allergic rhinitis evaluated in a nasal allergen challenge model as a prophylaxis therapy after 14 days of treatment.
- To evaluate the safety and tolerability of B244 relative to vehicle in subjects with allergic rhinitis after 14 days of treatment.
- To evaluate the efficacy of B244 relative to vehicle in treating individual nasal symptom scores in subjects with allergic rhinitis evaluated in a nasal allergen challenge model as a prophylaxis therapy after 14 days of treatment.

The exploratory objective is to test the hypothesis that B244 inhibits airway inflammation driven by nasal allergen challenge.

#### **1.3.1. Primary Endpoints**

Safety and tolerability will be assessed by reporting of AEs, physical examination and vital signs (blood pressure, heart rate, respiratory rate) during 14 days of treatment and up to 28 days of follow-up (Part 1).

### **1.3.2. Secondary Endpoints**

The secondary endpoints are:

- Change in TNSS from baseline to 14 days of prophylaxis treatment.
- Change in subjective nasal symptom scores of nasal congestion, rhinorrhea, nasal itching and sneezing from baseline to 14 days of prophylaxis treatment.
- Nasal symptom-free response rate within each individual symptom score and TNSS after 14 days of prophylaxis treatment.
- Safety and tolerability will be assessed in subjects with allergic rhinitis by reporting of AEs, physical examination and vital signs (blood pressure, heart rate, respiratory rate) during 14 days of treatment (Part 2).

### **1.3.3. Exploratory Endpoints**

The exploratory endpoints are:

- Change in Peak Nasal Inspiratory Flow (PNIF),
- Nasal inflammation score using otoscope,
- Intranasal nitric oxide levels, and
- Cytokine concentration in nasal cavity and blood from baseline to 14 days of B244 application and during prophylaxis treatment setting.

## **2. Detailed Statistical Methods**

### **2.1. General Statistical Methods**

This is a two-part study. Each of the two parts have 2 levels of active therapy ( $1 \times 10^9$  cells/ml and  $4 \times 10^9$  cells/ml) versus vehicle. The listings and tables will be presented separately for each of the two parts.

The collected data will be summarized using descriptive statistics (sample size, mean, standard deviation, median, minimum and maximum) or frequency counts, where appropriate, by treatment and overall.

For continuous variables, an Analysis of Covariance (ANCOVA) may be performed to test for significant differences between treatment groups. For discrete variables, the Cochran-Mantel-Haenszel Row Mean Score test will be used to test for significant differences between treatment groups.

## **2.2. Study Populations**

### Intent-to-Treat Population

All randomized patients will be included in the Intent-to-Treat Population.

### Safety Population

All subjects who received a single dose of the study medication will be included in the safety analysis population.

### Per Protocol Population

All subjects who administered at least 50% of study medication by weight, have at least one baseline and post baseline in clinic visit and did not have any major protocol violations will be included in the per protocol population.

## **2.3. Study Conduct and Baseline Characteristics**

### **2.3.1. Demographics and Subject Baseline Characteristics**

Demographic and subject baseline characteristics will be presented by treatment group and overall for each of the study populations. All continuous variables (age, baseline weight, height and body mass index (BMI)) will be summarized by descriptive statistics (number of observations, mean, standard deviation, median, minimum, maximum and coefficient of variation). All discrete variables (sex, race, ethnicity, childbearing status and tobacco/nicotine use) will be summarized by frequency counts and percentages. Data will also be shown in data listings by subject.

### **2.3.2. Study Drug Compliance**

The amount of study drug used by weight and the percent compliance by weight (actual weight of doses administered / expected weight of dose administered) will be summarized using descriptive statistics (number of observations, mean standard deviation, median, minimum and maximum) for each treatment group and overall. The number of doses administered will be summarized by frequency counts for each treatment group and overall.

### **2.3.3. Prior and Concomitant Medications**

Prior and concomitant medications will be summarized by frequencies and percentages. All medications will be coded using the World Health Organization (WHO) Drug dictionary September 2017 version.

Prior medications will be defined as any medication that started prior to the first day of administration. Concomitant medications will be defined as any medication that starts or is ongoing on or after the first day of administration. A medication may qualify as both a prior and concomitant medication if it started prior to first day of administration and is ongoing or stopped after the first day of administration.

Section 2.8 describes the imputation rules for partial dates. All medications will be presented in a data listing.

### **2.3.4. Total Nasal Symptom Score (TNSS) During Treatment**

The total nasal symptom score during treatment is collected for both part 1 and part 2 via subject diary. The total nasal symptom score is for monitoring purposes only and is part of study conduct (separate from the efficacy and safety assessments).

The total nasal symptom score will be summarized by each individual score (nasal congestion, sneezing, nasal itching and rhinorrhea) and total nasal symptom score for each study day by treatment group and overall.

The individual items will be summarized using frequency counts for each study day. Observed values and change from baseline (day 0 for Part 1, and the 0 minutes pre-NAC on day 14 for Part 2) will be summarized. A Cochran-Mantel-Haenszel test will be conducted at each study day to test for treatment effect.

The total nasal symptom score will be summarized using summary statistics for each study day. Observed values and change from baseline (if appropriate) will be summarized. An Analysis of Covariance with treatment as the factor and baseline value as a covariate will be used to test for treatment effect.

## **2.4. Safety Evaluations**

Safety is a primary endpoint for Part 1 of the study and is a secondary endpoint for Part 2 of the study. All of the safety tables will be presented in a similar fashion with the emphasis on primary and secondary endpoints covered in the CSR.

The following safety parameters will be tracked at designated intervals throughout the trial:

- Adverse Events,
- Laboratory Evaluations,
- Vital Signs,
- Physical Examinations,
- 12-Lead Electrocardiograms,
- Ambulatory Blood Pressure Monitoring, and
- Nasal Inspections.

### **2.4.1. Adverse Events / Serious Adverse Events**

Adverse events will be coded using the medical dictionary of regulatory activities (MedDRA Version 20.1) dictionary.

Treatment-emergent adverse events (TEAEs) will be defined as any AE that starts on or after the first administration of study medication. Any event that started prior to the first administration of study medication but worsened in severity after the first administration will be recorded as a new event so that it may be captured as a TEAE. AEs with an unknown onset date will be counted as treatment-emergent unless the event resolved prior to the first administration. Section 2.8 describes the imputation rules for partial dates.

Treatment-emergent adverse events that are documented as occurring within 30 minutes after any of the doses will be summarized with the other TEAEs and separately from the other TEAEs.

The incidence of TEAEs will be presented by system organ class (SOC) and preferred term (PT). Events will also be summarized by severity and relationship. The incidence of TEAEs leading to withdrawal from the study and SAEs, including deaths, will be presented in both summary tables and data listings.

All AEs will be presented in data listings.

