7.3 Study Withdrawal and Withdrawal from Investigational Product and Stopping Criteria

A participant may withdraw from the study at any time at his/her own request, or may be withdrawn at any time at the discretion of the Investigator.

Reasons for withdrawal (participants who refuse to complete any remaining study visits) or discontinuation (participants who prematurely stop the application) at any time during the study may include, but are not limited, to the following:

- For safety reasons, either at the discretion of the Investigator or at the participant's request
- For protocol violations at the discretion of AOBiome
- Due to concomitant therapy that could interfere with the results of the study (the Investigator will report all such information on the CRFs and decide, in accordance with AOBiome, whether the participant is to be withdrawn).

The reason for participant study withdrawal will be recorded in the electronic Case Report Form (eCRF). Data from participants withdrawing from the study will be considered evaluable up to the point at which they are withdrawn using the same criteria for evaluability as for participants who complete the study.

For Part 1 safety evaluation and Part 2 preliminary efficacy , AOBiome will include study stopping rules to pause study for safety review in the event that ~~t1~~ subject reports a SAE, ~~t2~~ grade 3 (severe) AEs, or ~~t3~~ grade 2 (moderate) AEs considered possibly, probably, or definitely related to the investigational product.

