14.4 Safety Analyses

14.4.1 Definitions

All adverse events recorded during the study will be coded according to Medical Dictionary for Regulatory Activities.

The primary analysis of safety will be based on the safety population, which is defined as all subjects receiving at least 1 dose of B244 or placebo. Adverse events (AEs) will be coded using the Medical Dictionary for Regulatory Activities (MedDRA®) for purposes of summarization. All AEs occurring during the study will be included in by-subject data listings and tabulated. Events leading to death, SAEs, and events resulting in study discontinuation will be summarized using standard descriptive statistics, and presented by treatment arm. Exposure to study drug and reasons for discontinuation of study treatment will be tabulated. Shift tables relative to the normal range will be provided for laboratory parameters. Additional analyses will be performed, if warranted, upon review of the data.

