14.4.4 Adverse Events Leading to Treatment Discontinuation

Adverse events leading to treatment discontinuation will be summarized overall and by primary system organ class and preferred term.

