## 2.9. Subject Withdrawals

Subject withdrawals will be summarized in a disposition table for all subjects. The reasons for discontinuation will also be tabulated. Withdrawals due to AEs will be tabulated as discussed in the Adverse Event section above. A listing of the subjects who withdrew due to an AE will be presented as well as a listing of the subjects’ completion and/or discontinuation status.

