## 3. Data Listing Shells

### 3.1. Data Listings Table of Contents

The following post-text listings will be generated.

Listing Number	Listing Title
16.2.1-1	Subject Completion / Discontinuation – Part 1
16.2.1-2	Subject Completion / Discontinuation – Part 2
16.2.2-1	Protocol Deviations – Part 1
16.2.2-2	Protocol Deviations – Part 2
16.2.3.1-1	Demographics and Baseline Characteristics – Part 1
16.2.3.1-2	Demographics and Baseline Characteristics – Part 2
16.2.3.2-1	Subject Eligibility and Informed Consent – Part 1
16.2.3.2-2	Subject Eligibility and Informed Consent – Part 2
16.2.3.3-1	Medical History / Surgical History / Procedures – Part 1
16.2.3.3-2	Medical History / Surgical History / Procedures – Part 2
16.2.3.4-1	Prior and Concomitant Medications – Part 1
16.2.3.4-2	Prior and Concomitant Medications – Part 2
16.2.3.5-1	Substance Use – Part 1
16.2.3.5-2	Substance Use – Part 2
16.2.4.1-1	Study Drug Administration – Part 1
16.2.4.1-2	Study Drug Administration – Part 2
16.2.4.2-1	Dose Compliance Log – Part 1
16.2.4.2-2	Dose Compliance Log – Part 2
16.2.5.1-1	Total Nasal Symptom Score (TNSS) During Treatment – Part 1
16.2.5.1-2	Total Nasal Symptom Score (TNSS) During Treatment – Part 2
16.2.5.2-1	Individual Nasal Symptom Items During Treatment – Part 1
16.2.5.2-2	Individual Nasal Symptom Items During Treatment – Part 2

Listing Number	Listing Title
16.2.5.3-2	Total Nasal Symptom Score (TNSS) During NAC – Part 2
16.2.5.4-2	Individual Nasal Symptom Items During NAC – Part 2
16.2.5.3-1	Peak Nasal Inspiratory Flow – Part 1
16.2.5.3-2	Peak Nasal Inspiratory Flow – Part 2
16.2.5.4-1	Nasal Inflammation Score – Part 1
16.2.5.4-2	Nasal Inflammation Score – Part 2
16.2.5.5-1	Intranasal Nitric Oxide – Part 1
16.2.5.5-2	Intranasal Nitric Oxide – Part 2
16.2.6.1-1	Adverse Events – Part 1
16.2.6.1-2	Adverse Events – Part 2
16.2.6.2-1	Adverse Events Leading to Discontinuation of Study – Part 1
16.2.6.2-2	Adverse Events Leading to Discontinuation of Study – Part 2
16.2.6.3-1	Serious Adverse Events – Part 1
16.2.6.3-2	Serious Adverse Events – Part 2
16.2.7.1-1	Laboratory Results – Hematology – Part 1
16.2.7.1-2	Laboratory Results – Hematology – Part 2
16.2.7.2-1	Laboratory Results – Chemistry – Part 1
16.2.7.2-2	Laboratory Results – Chemistry – Part 2
16.2.7.3-1	Laboratory Results – Urinalysis – Part 1
16.2.7.3-2	Laboratory Results – Urinalysis – Part 2
16.2.7.4-1	Laboratory Results – Other – Part 1
16.2.7.4-2	Laboratory Results – Other – Part 2

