14.3.1.3-2	Summary of Treatment Emergent Adverse Events by Body System, Preferred Term and Severity – Safety Population - Part 2
14.3.1.4-1	Summary of Treatment Emergent Adverse Events by Body System, Preferred Term and Relationship to Study Medication – Safety Population - Part 1
14.3.1.4-2	Summary of Treatment Emergent Adverse Events by Body System, Preferred Term and Relationship to Study Medication – Safety Population - Part 2
14.3.1.5-1	Summary of Immediate Treatment Emergent Adverse Events by Body System and Preferred Term – Safety Population - Part 1
14.3.1.5-2	Summary of Immediate Treatment Emergent Adverse Events by Body System and Preferred Term – Safety Population - Part 2
14.3.1.6-1	Summary of Delayed Treatment Emergent Adverse Events by Body System and Preferred Term – Safety Population - Part 1
14.3.1.6-2	Summary of Delayed Treatment Emergent Adverse Events by Body System and Preferred Term – Safety Population - Part 2
14.3.1.7-1	Summary of Adverse Events Leading to Study Discontinuation – Safety Population - Part 1
14.3.1.7-2	Summary of Adverse Events Leading to Study Discontinuation – Safety Population - Part 2
14.3.1.8-1	Summary of Serious Adverse Events – Safety Population - Part 1
14.3.1.8-2	Summary of Serious Adverse Events – Safety Population - Part 2
14.3.2.1-1	Summary of Laboratory Evaluations – Hematology – Safety Population - Part 1

Table Number	Table Title
14.3.2.1-2	Summary of Laboratory Evaluations – Hematology – Safety Population - Part 2
14.3.2.2-1	Summary of Laboratory Evaluations – Chemistry – Safety Population - Part 1
14.3.2.2-2	Summary of Laboratory Evaluations – Chemistry – Safety Population - Part 2
14.3.2.3-1	Summary of Laboratory Evaluations – Urinalysis – Safety Population - Part 1
14.3.2.3-2	Summary of Laboratory Evaluations – Urinalysis – Safety Population - Part 2
14.3.2.4-1	Summary of Laboratory Evaluations – Other – Safety Population - Part 1
14.3.2.4-2	Summary of Laboratory Evaluations – Other – Safety Population - Part 2
14.3.3-1	Summary of Vital Signs – Safety Population - Part 1
14.3.3-2	Summary of Vital Signs – Safety Population - Part 2
14.3.4-1	Summary of Electrocardiograms – Safety Population - Part 1
14.3.5-1	Summary of Ambulatory Blood Pressure Monitoring – Safety Population - Part 1

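### The SAP specifies outputs for AEs leading to study withdrawal but none for AEs leading to treatment discontinuation, which Protocol 14.4.4 requires by SOC and PT

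*SAP*

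**What the plan says.** **Protocol.** Sections 7.3 and 12.6 name two events. One is withdrawal, meaning refusal of the remaining visits. The other is "discontinuation (participants who prematurely stop the application". Three requests then follow in the safety analysis sections:

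- Section 14.4.4: "Adverse events leading to treatment discontinuation will be summarized overall and by primary system organ class and preferred term".
- Section 14.4.1: "Exposure to study drug and reasons for discontinuation of study treatment will be tabulated".
- Section 14.4.1 also asks for a summary of events that result in discontinuing the study.

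Sections 14.3 and 14.4.2 ask for discontinuations due to AEs without saying which kind. Section 14.3.1 asks for reasons for discontinuing the study.

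**SAP.** Section 2.4.1 says: "The incidence of TEAEs leading to withdrawal from the study and SAEs, including deaths, will be presented in both summary tables and data listings". Table 14.3.1.7-1 is titled "Summary of Adverse Events Leading to Study Discontinuation – Safety Population - Part 1" and Listing 16.2.6.2-1 is titled "Adverse Events Leading to Discontinuation of Study – Part 1". The Part 2 versions (14.3.1.7-2 and 16.2.6.2-2) match. Section 2.9 begins: "Subject withdrawals will be summarized in a disposition table for all subjects". It goes on to say that reasons for discontinuation will be tabulated, without stating whether that means treatment or study. For withdrawals due to AEs it refers back to the adverse event section.

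**The concern.** The primary objective is the safety and tolerability of B244 relative to vehicle in Part 1, and the same assessment is secondary in Part 2. Stopping the spray because of an AE is one of the most direct tolerability results such a trial can give. Under the SAP as written, whether such a subject enters the AE-discontinuation table depends on whether he or she also stops attending. Someone who stops and leaves is counted. Someone who stops and keeps coming is not, and is also a completer under Protocol 12.4, which defines completion by visits alone. The count then partly measures willingness to return, and a comparison of B244 with vehicle on it could understate intolerance in either arm.

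**Working it through.** The check is mainly a comparison of text. The plan states no figure on this point, so there is none to reproduce.

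**Step 1. Match each protocol request to a SAP output.**

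| Protocol request | SAP output | Met? |
|---|---|---|
| 14.4.1, events resulting in study discontinuation | 2.4.1; Tables 14.3.1.7-1/-2; Listings 16.2.6.2-1/-2 | Yes |
| 14.3.1, reasons for study discontinuation | 2.9 and the disposition tables | Yes |
| 14.4.1, reasons for stopping study treatment | 2.9, if its reasons include treatment | Unclear |
| 14.4.4, AEs leading to treatment discontinuation, overall and by SOC and PT | None named in the text, table list or listing list | No |

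**Step 2. Follow one case through the SAP.** Take a subject who stops the spray for an AE during the 14 days but attends every later visit.

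- The AE enters the TEAE tables by SOC and PT, severity and relationship, and the listing of all AEs.
- The stop can be seen in the dose counts, the compliance by weight, and the Study Drug Administration and Dose Compliance Log listings.
- The subject is not in Tables 14.3.1.7 or Listings 16.2.6.2, because he or she did not leave the study.
- On a generous reading of SAP 2.9, an AE might be tabulated as the reason for stopping. That would still not be by SOC and PT.

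So the components are reported, but no output is specified to link the stop to the AE in the form that 14.4.4 asks for.

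**Step 3. Scale, as illustration only.** Inputs: 8 active subjects per dose cohort in Part 1, so 16 active in all, and 14 per arm in Part 2 (Protocol 14.1). One uncounted subject moves a rate by 1/n. Intervals are exact (Clopper-Pearson) 95%.

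- Part 1 dose group: 1/8 = 12.5 points. The reported rate is 0/8 (0%, interval 0 to 36.9%) instead of 1/8 (12.5%, 0.3 to 52.7%).
- Part 1 active groups pooled: 1/16 = 6.3 points.
- Part 2 arm: 1/14 = 7.1 points. The reported rate is 0/14 (0%, 0 to 23.2%) instead of 1/14 (7.1%, 0.2 to 33.9%).

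**Step 4. How likely is at least one case?** The documents give no rate p for stopping treatment because of an AE while staying in the study, so p is assumed. The chance of at least one case is 1 − (1 − p)^n.

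| Assumed p | Part 1 active, n = 16 | Part 2 arm, n = 14 |
|---|---|---|
| 2% | 1 − 0.98^16 = 27.6% | 1 − 0.98^14 = 24.6% |
| 5% | 1 − 0.95^16 = 56.0% | 1 − 0.95^14 = 51.2% |
| 10% | 1 − 0.90^16 = 81.5% | 1 − 0.90^14 = 77.1% |

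**The case against.** The case for leaving the SAP alone has four parts.

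- **The protocol's own terms are mixed.** Section 14.4.1 asks for study discontinuation as well as reasons for stopping treatment, and 14.3 and 14.4.2 do not specify. This stands, and it means the SAP follows one explicit protocol request. It does not discharge 14.4.4, which names treatment.
- **SAP 2.9 may already cover stopping treatment.** If its reasons for discontinuation carry the meaning in Protocol 7.3, reasons for stopping the spray would be tabulated. This stands as an ambiguity. It would answer 14.4.1 but not the SOC and PT summary in 14.4.4.
- **The information is not lost.** Protocol 8.6 requires reasons for missed doses in the eCRF, Protocol 12.6 requires premature discontinuations and their causes to be documented, and SAP 3.2 lists all subjects and all data. With 24 and 42 subjects, a careful reader of the listings could find the case. This stands. What is lacking is a specified summary.
- **The affected group may be small or empty.** Treatment lasts 14 days. Subjects who need rescue medication leave the study under Protocol 8.14 and so fall in the SAP's category. No separate visit schedule is given for subjects who are off treatment but still attending. This also stands, although 7.3 and 12.6 allow for such subjects.

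A reader might infer that the SAP has replaced every treatment-level request with study withdrawal, or that such a subject disappears from the report. The documents do not support either reading, for the reasons in the second and third points.

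**Conclusion.** The gap is real and specific. Protocol 14.4.4 requires a summary that the SAP's text, table list and listing list do not contain, and the SAP gives no reason for leaving it out. The missing output bears on the primary objective. The conclusion rests on the distinction in Protocol 7.3 and 12.6 and on reading the SAP's titles at face value.

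Its numerical size cannot be established. The 12.5 and 7.1 points show how coarse the arms are; they do not estimate an undercount. A reader might take them as an expected bias, but no rate in the documents supports that. No design figure, test or population changes. This should be corrected before the Part 1 lock and unblinding, so that what counts as a treatment discontinuation due to an AE is settled while the data are blinded.

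**What to change.** 1. Keep SAP 2.4.1, Tables 14.3.1.7-1/-2 and Listings 16.2.6.2-1/-2 for study withdrawal. Protocol 14.4.1 asks for them.
2. Add to SAP 2.4.1, 3.1 and 4.1, for each part, one table and one listing of TEAEs leading to discontinuation of study treatment. The table should give the overall count and then SOC and PT by treatment group in the Safety Population.
3. State in SAP 2.9 that reasons for stopping treatment are tabulated separately from reasons for leaving the study.
4. Name the source: the discontinuation causes required by Protocol 12.6 and the missed-dose reasons required by Protocol 8.6. Whether the eCRF has an item tying a specific AE to the stop cannot be seen from the documents. If it has none, the SAP should say how the link is made from these records before unblinding.

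The cost is two tables, two listings, some wording, and an added block of reasons in the disposition tables. No visit, procedure or sample size changes.
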